#### 1.0 Introduction

Intensive care will soon represent 2% of the United States' gross domestic product, and nearly two-thirds of intensive care unit (ICU) days are accounted for by people over 65 years old. The population of aging Americans filling our ICUs is especially vulnerable to the development and persistence of delirium. We and others have shown ICU delirium to independently predict a 3-fold higher mortality within a year, longer hospital stays, much higher costs of care, and long-term cognitive impairment. Delirium, a form of acute brain dysfunction, develops in 7 out of 10 mechanically ventilated patients in general medical and surgical ICUs. 7,15-18 Delirium's high prevalence and independent relationship with poor outcomes in critically ill patients have led to numerous recommendations that delirium monitoring be part of the standard daily assessment in all ICU patients. 19-21 Delirium is usually multifactorial, 22,23 and treatment of underlying disturbances represents first-line management. Even after addressing modifiable risk factors for ICU patients, however, delirium often persists from a few days to months. Antipsychotics are recommended as the medication class of choice for delirium by all major clinical guidelines,  yet very little evidence exists to support this internationally recognized and adopted treatment. 25-28 Because the vast population of older ICU patients are at very high risk for delirium, millions of older patients around the world receive significant amounts of intravenous antipsychotic medications for delirium despite the fact that no placebo-controlled trial has definitively demonstrated efficacy or safety of these medications for ICU delirium. Tens of thousands of ICU patients receive antipsychotics for delirium every day with limited evidence to establish best practice for effective pharmacologic management of this debilitating syndrome. Haloperidol, a "typical" antipsychotic, is the most commonly chosen, used by 86% of ICU practitioners. 29,30 Atypical antipsychotics, of which there are currently eight available in the U.S., are the next most commonly utilized drug for delirium in ICUs; 38% of practitioners use atypicals. Despite their popularity, the use of antipsychotics for delirium remains controversial. Concerns about the safety of these drugs are fueled by well-known toxicities, including lethal cardiac arrhythmias and extrapyramidal symptoms, as well as reports of increased death rates associated with antipsychotic use in ambulatory geriatric populations. 31-37 The MIND-USA study is a multicenter, double-blind, randomized, placebo-controlled trial investigating the effects of intravenously (IV) administered typical and atypical antipsychotics (haloperidol and ziprasidone) on delirium in critically ill patients, many of whom are older than 70 years. This study will have adequate (> 80%) power to detect a therapeutic difference between haloperidol and an atypical antipsychotic (ziprasidone) versus placebo in a broad adult ICU population and within important subgroups such as severely ill older patients with significant comorbidities. In the burgeoning field of aging brain research which involves the disciplines of medicine, surgery, geriatrics, psychiatry, critical care, neuroscience, nursing, and clinical pharmacology—this timely interdisciplinary investigation of a common, expensive, deadly condition without known effective therapy will both direct clinical practice and shape future work.

MIND-USA Protocol Version: 1.15 Confidential Protocol Date: June 22, 2016 3 of 51

**Hypothesis**: The administration of typical (haloperidol) and atypical (ziprasidone) antipsychotics to critically ill patients with delirium will improve short- and long-term clinical outcomes.

### **Specific Aims**

- **Aim 1**: To determine whether haloperidol or ziprasidone administered to delirious medical/surgical ICU patients will increase days alive without delirium (measured as delirium/coma-free days [DCFDs]) over a 14-day study period compared with placebo and compared with one another.
- **Aim 2**: To determine whether haloperidol or ziprasidone will improve 30-day, 90-day, and 1-year survival compared with placebo and compared with one another.
- **Aim 3**: To determine whether haloperidol or ziprasidone will reduce ICU length of stay (LOS) (i.e., time to ICU discharge) compared with placebo and compared with one another.
- **Aim 4**: To determine whether haloperidol or ziprasidone will improve long-term neuropsychological outcomes, functional independence, quality of life, and posttraumatic stress disorder symptoms at 3-month and 1-year follow-up compared with placebo and compared with one another.

To complete these Aims, we will consent adult medical and surgical ICU patients (a) on mechanical ventilation or non-invasive positive pressure ventilation, and/or (b) in shock requiring vasopressors. Once delirium occurs, we will randomize a total of 561 delirious patients (187 to the haloperidol group, 187 to the ziprasidone group, and 187 to the placebo group) and follow them for 1 year. In the absence of an indication requiring hold of study drug, patients will receive study drug until delirium has resolved for two days or ICU discharge or 14 days after the day of randomization, whichever occurs first. While tracking **primary** (delirium duration, Aim 1) and **secondary outcomes** (mortality, ICU LOS, and long-term neuropsychological function; Aims 2-4), we will closely monitor safety parameters, including arrhythmias, extrapyramidal symptoms (EPS), neuroleptic malignant syndrome (NMS), and posttraumatic stress disorder (PTSD). **The study sample size was explicitly chosen to ensure adequate power** ( $\geq$  80%) to **detect the effect of antipsychotics in four important subgroups**: age  $\geq$  70 years, high severity of illness (APACHE II  $\geq$  25), presence of severe sepsis at enrollment, and medical vs. surgical ICU patients. We will also conduct hypothesis-generating subgroup analyses of the effect of antipsychotics on delirium in patients with pre-existing cognitive impairment.

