Atypical antipsychotic agents, compared with haloperidol, have a wider variety of reported affinities for CNS receptors, including dopamine, serotonin, adrenergic, and muscarinic receptors.  $^{107,125}$  Ziprasidone an antagonist at  $D_2$ ,  $H_1$ ,  $\alpha_1$ ,  $5\text{-HT}_{2A}$ ,  $5\text{-HT}_{2C}$ , and  $5\text{-HT}_{1D}$  receptors and an agonist at  $5\text{-HT}_{1A}$  receptors.  $^{125,126}$  Like other successful antipsychotic medications, it has high affinity for the  $D_2$  receptor, though this is not the majority of its receptor activity (as seen with haloperidol). It is distinguished from other atypicals by blocking reuptake of norepinephrine and  $5\text{-HT}.^{126}$  As stated above, atypical antipsychotics typically have a lower incidence of EPS versus haloperidol.  $^{112,127}$  A high  $5\text{HT}_{2A}/D_2$  receptor affinity ratio, which is a particularly strong characteristic of ziprasidone, has been correlated with lower propensity for EPS and may be advantageous in treating negative symptoms  $^{126}$  so prevalent in hypoactive delirium. The  $\alpha_1$  receptor affinity of ziprasidone is reduced in comparison to other atypical antipsychotic medications, which may translate into less orthostatic hypotension. It increases central nervous system acetylcholine and through agonism at the  $5\text{HT}_{1A}$  receptor (as seen with the antidepressant and anxiolytic buspirone) can increase dopamine in the cortex, both of which theoretically would be helpful for delirium.

The strikingly divergent receptor affinities of these two classes of antipsychotics adds to the clinical conundrum surrounding the fact that they are both used anecdotally in widely varying rates across the country for treatment of delirium. Thus, in addition to being the first ever adequately powered trial to compare antipsychotics vs. placebo for ICU delirium, MIND-USA will also be a major step toward making evidence-based decisions about which class of antipsychotics is most effective for critically ill delirious patients. Lastly, the trial may begin to shed light on the complex and poorly understood neurophysiologic derangements underlying delirium in critically ill patients. 

MIND-USA Protocol Version: 1.15 Confidential Protocol Date: June 22, 2016 8 of 51

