- 11.4 Data Analysis Plan. To assess success of randomization, the distribution of baseline factors, such as age, sex, race, severity of illness, and sepsis, will be assessed by comparing summary measures between patients randomized into the 3 groups to identify clinically meaningful differences rather than relying on statistical testing. The primary outcome of the Aim 1 analysis is delirium/coma-free days, which we will examine using both unadjusted and adjusted analyses. To determine the unadjusted effect of antipsychotic administration on this and other continuous outcomes, we will utilize the Kruskal-Wallis test to compare delirium/coma-free days between the three treatment groups. If the test is significant, we will use pairwise Wilcoxon rank-sum tests to compare each of the two antipsychotics groups directly to the placebo group. To determine the unadjusted effect of antipsychotic administration on ICU length of stay, survival, and other time-to-event outcomes, the cumulative incidence probability of these outcomes will be estimated via Kaplan-Meier product limit method, and the log-rank test will be used to compare the three groups.

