2.2 Objectives

The MIND-USA study is a multicenter, double-blind, randomized, placebo-controlled trial investigating the effects of intravenously (IV) administered typical and atypical antipsychotics (haloperidol and ziprasidone) on delirium in critically ill patients. The study evaluates the following aims:

- Aim 1: To determine whether haloperidol or ziprasidone administered to delirious medical/surgical ICU patients will increase days alive without delirium and coma (measured as delirium/coma-free days [DCFDs]) over a 14-day study period compared with placebo.
- **Aim 2:** To determine whether haloperidol or ziprasidone will improve 30-day, 90-day, and 1-year survival compared with placebo.
- **Aim 3:** To determine whether haloperidol or ziprasidone will reduce ICU length of stay (LOS) (i.e., time to ICU discharge) compared with placebo.
- Aim 4: To determine whether haloperidol or ziprasidone will improve long-term neuropsychological outcomes, functional independence, quality of life, and post-traumatic stress disorder symptoms at 3-month and 1-year follow-up compared with placebo.

3. Study Methods

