All in-hospital outcomes will be analyzed using both univariate methods and multivariable regression, adjusting for covariates noted below. Though patient characteristics should theoretically be balanced between treatment groups due to randomization, adjustment increases our power and precision. Though we will perform both types of analyses for each outcome, adjusted analyses will be considered the primary analysis.

Unadjusted Analyses

In-Hospital Continuous Outcomes

We will analyze continuous outcomes (delirium/coma-free days [PO]; delirium duration [total, SO2; hyperactive and hypoactive delirium separately; coma duration; mean CV SOFA and lowest mean arterial pressure]) using the Kruskal-Wallis test. These outcomes are typically not normally distributed; therefore, the assumptions for a parametric ANOVA would be violated, and results would be unreliable. The nonparametric Kruskal-Wallis test does not assume that the outcome has a normal distribution, and thus provides more power and reliability in the case of a non-normal distribution.

If the unadjusted test for the primary outcome (DCFDs) only is statistically significant, we will use Dunn's test for pairwise differences between treatment groups, using a Bonferroni correction for multiple comparisons at a 2.5% alpha level.

Time to Event Outcomes

We will describe and test for differences in time to death (**SO1**) using Kaplan-Meier curves and the log-rank test, respectively. ICU and hospital discharge, liberation from mechanical ventilation, and ICU readmission all have a competing risk of death (**SO3**, **SO4**, **SO5**, and **SO6**, respectively). (For ICU readmission and liberation from mechanical ventilation, hospital discharge without experiencing the outcome will be treated as an additional competing risk.) Therefore, we will describe the cumulative incidences of both the outcome of interest and each competing risk, along with a modified chi-squared test for the difference between groups in the subdistribution of interest (Gray 1988). Patients who withdrew in the hospital with no discharge or death information available are censored at the time of withdrawal; we censor at x.01 days anyone who has experienced neither death nor the outcome of interest by x days (where x is the end of the time frame specified above for each outcome). We will detail how many and when patients were censored for each analysis.

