"Time 0" will be the time of randomization for each of these outcomes, with the exception of ICU readmission; for this outcome, "time 0" will be the time of the first ICU discharge, and only patients who survived their first ICU admission will be included.

Long-Term Outcomes

We will use multivariable regression to analyze the relationship between treatment group and scores measuring long-term neuropsychological, quality of life, and PTSD outcomes as outlined in the Outcomes section above. Depending on the distribution of each outcome, we will use linear regression, negative binomial regression, or proportional odds logistic regression, as appropriate. These models will not include covariates other than treatment.

For each outcome, we will have separate models for 3- and 12-month scores. At each time point, we include all patients with available outcome data, using inverse probability weighting to account for patient death and attrition. To decrease reliance on a few highly influential observations, we will truncate weights at the top 1 percentile.

As a sensitivity analysis, we will also define long-term outcomes using the unadjusted composite endpoint approach (reference: Lachin) to deal with outcomes truncated due to death or loss to follow up. The composite endpoint will be defined as:

- If the patient dies prior to assessment: days between randomization and death
- If the patient survives and is successfully assessed: days between randomization and planned assessment (constant) + assessment score

For example, if we are analyzing a 3-month outcome, the constant would be 90. Differences between the composite end point distribution amongst groups will be assessed using the Kruskal-Wallis test.

Adjusted Analyses

We will adjust all coefficient variances using Huber-White sandwich estimation, clustered by study site. This will help account for unmeasured variability and correlation among patients within a given site.

In-Hospital Continuous Outcomes

We will use proportional odds logistic regression for continuous outcomes (delirium/coma-free days; delirium duration [any, hyperactive, and hypoactive]; coma duration; mean CV SOFA and lowest mean arterial pressure); this method assumes an ordinal outcome but does not assume that it follows a specific statistical distribution.

If the overall test for treatment vs our primary outcome (DCFDs) is significant at the 5% level, we will report individual treatment tests vs placebo at the 2.5% level.

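### All four protocol aims promise a haloperidol–ziprasidone comparison, but the SAP drops it without a reason and no primary analysis specifies an estimate of it

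*Protocol*

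**What the plan says.** **Aims.** Protocol 1.0 (Specific Aims) gives each aim two comparisons: each drug with placebo, and the drugs with each other. Aim 1 reads "over a 14-day study period compared with placebo and compared with one another"; Aim 2 reads "30-day, 90-day, and 1-year survival compared with placebo and compared with one another"; Aims 3 and 4 close the same way. Protocol 2.4 adds that the trial will be a "major step toward making evidence-based decisions about which class of antipsychotics is most effective". In SAP 2.2, Aim 1 becomes "over a 14-day study period compared with placebo" and stops there. SAP Aims 2 to 4 are shortened in the same way, without explanation.

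**DCFDs.** Protocol 11.1 and SAP 3.3 size the trial for two pairwise comparisons, each drug against placebo, at two-sided 2.5%. After a significant Kruskal-Wallis test, Protocol 11.4 uses Wilcoxon tests to "compare each of the two antipsychotics groups directly to the placebo group". SAP 7 makes the adjusted analysis primary; after a significant overall test, "we will report individual treatment tests vs placebo at the 2.5% level". The SAP's unadjusted rule is worded differently: Dunn's test "for pairwise differences between treatment groups, using a Bonferroni correction for multiple comparisons at a 2.5% alpha level".

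**Aims 2 to 4.** Protocol 11.4 and SAP 7 give three-group tests (log-rank, Gray's test) and regressions with treatment as a term. Neither document names a pairwise contrast, whether against placebo or between drugs. The SAP 3.3 power statements for mortality and ICU stay use a 1.67% level; Protocol 11.2 uses 2.50% for the same outcomes.

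**The concern.** A question stated in every protocol aim has no planned estimate in any primary analysis. If one drug separates from placebo and the other does not, readers will tend to rank the drugs. A difference in significance between two placebo contrasts is not a test of one drug against the other. If the direct contrast is added later, it will have been chosen after results were seen. Yet Protocol 11.4 and SAP 4 both justify leaving secondary outcomes unadjusted on the ground that each comparison is driven by a hypothesis.

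The primary placebo question is not affected. What is at stake is whether a stated objective is answered, withdrawn openly, or left to post hoc inference.

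**Working it through.** **1. Which planned analyses could give a haloperidol–ziprasidone result?**

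| Outcome | Planned analysis | Between-drug result? |
|---|---|---|
| DCFDs, protocol | Kruskal-Wallis, then Wilcoxon tests against placebo | No |
| DCFDs, SAP primary (adjusted) | Proportional odds model, then tests against placebo at 2.5% | No |
| DCFDs, SAP unadjusted | Kruskal-Wallis, then Dunn's pairwise tests | Possibly; a gated test with no effect estimate |
| Survival, ICU stay | Log-rank or Gray's test; Cox or Fine-Gray model | No pairwise contrast named |
| Long-term outcomes | Weighted regressions on treatment group | No pairwise contrast named |

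**2. Reproduce the plan's own figure.** Inputs from Protocol 11.1: SD 5.2, 187 per arm, a 2-day difference, two-sided 2.5%.

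- SE = 5.2 × √(2/187) = 0.538 day.
- Power = Φ(δ/SE − z) = Φ(2/0.538 − 2.241) = Φ(1.48) = 93.0%.

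The plan states 92%. A Wilcoxon efficiency of 0.955 (an assumption that fits normal data) gives 91.8%. The stated power therefore matches a level of 0.05/2, which is two contrasts.

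**3. Precision of the between-drug contrast.** Allocation is 1:1:1, so the SE is again 0.538. The 95% half-width is 1.96 × 0.538 = 1.05 days.

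**4. Power of the between-drug contrast.** The documents assume no drug-versus-drug difference, so a range is shown.

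| True difference (days) | Two-sided 5% | 2.5% | 1.67% |
|---|---|---|---|
| 0.5 | 15% | 10% | 7% |
| 1.0 | 46% | 35% | 30% |
| 1.5 | 80% | 71% | 65% |
| 2.0 | 96% | 93% | 91% |

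**5. How many contrasts did the authors have in mind?** 0.05/2 = 0.025 fits the DCFD sizing. 0.05/3 = 0.0167 fits the SAP's mortality and ICU-stay level, and so fits three pairs. That is an inference from the number; the text of SAP 3.3 does not say it.

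**6. Does Dunn's test on three pairs at 2.5% inflate error?** Normal arm means were simulated 200,000 times, with a 5% global test followed by all three pairs at 2.5%. With no true differences, the chance of any false pairwise finding was 4.8%. With both drugs 2 days better than placebo and equal to each other, the false between-drug rate was 2.5%. The simulation shows no inflation in these cases.

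**The case against.** The strongest case on the other side is that this is a placebo-controlled trial and says so. Protocol 4.1 states the primary objective against placebo, 2.7 calls placebo the primary comparator, and 1.0 and 2.4 already describe adequate power as against placebo. On that view the SAP only brings its aims into line with its primary analysis. This stands as context. It also shows that the conflict begins inside the protocol, between its aims and its sections 11.1 and 11.4. It does not remove the comparison from four numbered aims.

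A reader might also infer more than the documents support:

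- **That only placebo contrasts are planned and nothing addresses the drug pair.** As worded, Dunn's test includes that pair for DCFDs. For Aims 2 to 4 the accurate description is that contrasts are unspecified, not that they are limited to placebo.
- **That Dunn's test at 2.5% on three pairs is a multiplicity fault.** The global test comes first, and the simulation shows 4.8% under the global null. The fault is inconsistency between the unadjusted and adjusted rules.
- **That the trial cannot rank the drugs.** This depends on the size of the difference: power is low at 0.5 to 1 day and high at 2 days.
- **That results drove the narrowing.** SAP 8 describes its missing-data counts as taken before unblinding, and SAP 3.2 places unblinding after data cleaning. Nothing points to a results-driven change.

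**Conclusion.** The concern holds in this form: the protocol's aims and the SAP's aims conflict without explanation, and no primary analysis of any aim specifies a head-to-head estimate. For DCFDs the possible exception is an unadjusted, gated, non-primary test that gives no effect size. For Aims 2 to 4 no pairwise contrast is specified.

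The contrast would be informative but only moderately precise: about ±1.05 days, with 80% power at two-sided 5% for a difference of about 1.5 days. Any statement about ranking the two drugs must be conditional on the size of the difference. These figures assume SD 5.2 in both drug arms, 187 per arm and a comparison of means. The primary model is proportional odds, so they are a guide to scale and not the interval that would be reported. The matter should be settled before unblinding; it does not threaten the placebo comparisons.

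**What to change.** Choose one of two courses and record the reason.

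1. **Keep the objective.** Restore it in SAP 2.2. Before unblinding, prespecify the haloperidol–ziprasidone contrast with its 95% confidence interval for each aim, taken from the adjusted models already planned (proportional odds, Cox, Fine-Gray and the long-term regressions). Label it secondary and estimation-only, and leave the two placebo contrasts at 2.5%.
2. **Withdraw the objective.** Remove the between-drug clause from Protocol Aims 1 to 4, state why, and bring the choice-of-class sentence in Protocol 2.4 into line.

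Under either course, state which pairs Dunn's test covers so that the SAP's unadjusted and adjusted DCFD rules agree, and name the pairwise contrasts to be reported for Aims 2 to 4.

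The cost is one linear contrast per model plus wording, with no extra patients or data. The small downside of the first course is one more interval per outcome, of modest precision.

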# 2.0 Background

"For many aging people in good physical condition, who succumb to an acute illness, cognitive decline [e.g., delirium followed by an acquired post-ICU long-term cognitive impairment] is the main threat to their ability to recover and enjoy their favorite activities; for those whose physical activities were already limited, cognitive decline is a major additional threat to quality of life."

-National Research Council

[figure not shown]
"In patient populations for whom the evidence of the efficacy of antipsychotic medications is limited...prudence would suggest that the use of these drugs should be reduced sharply."

-January 2009 NEJM (yet data show sharp increases in ICU use recently)

MIND-USA Protocol Version: 1.15 Confidential Protocol Date: June 22, 2016 4 of 51

**2.1 The Magnitude of the Problem of Delirium in Critically Ill Patients.** Delirium is a syndrome of acute organ dysfunction occurring in 50% to 80% of ICU patients.  The DSM IV-TR^46 and the CAM-ICU define delirium as an acute form of brain dysfunction characterized by a change in baseline mental status and inattention, plus disorganized thinking or

an altered level of consciousness as noted in **Figure 1**, which distinguishes delirium from coma, and highlights the cardinal symptoms of delirium. A **dashed line** encircles optional symptoms of delirium (i.e., those sometimes present but not mandatory a diagnosis of delirium). Whereas "respiratory failure" is the most common reason for ICU admission across ages, delirium (i.e., brain "failure") is the classic geriatric syndrome serving as the strongest determinant of hospitalized patients' length stay and disposition. Delirium in ICU

patients carries enormous financial and societal burdens due to its association with increased morbidity, mortality,  and prolonged hospital stays,  as well as its relationship to long-term neuropsychological deficits among ICU survivors.  In fact, the occurrence of ICU delirium predicts a 3- to 13-fold rise in the likelihood of death by 1 year after adjusting for severity of illness, coma, sedatives, and other relevant covariates.  In addition, each additional day of delirium independently increases the risk of death by 10% (p=0.03), strongly supporting Aims 1 and 2 of the MIND-USA study. It is estimated that ICU delirium is associated with costs ranging from \$4 to \$16 billion annually in the U.S. alone, 12 not including added cost of lost workdays, caregiver burden, or cognitive rehabilitation for the 66% of patients with ongoing neuropsychological deficits at 6 months and the 50% with ongoing deficits at 24 months following their ICU stay.  Due to the increased utilization of intensive care and our aging population, who have multiple medical problems, pre-existing cognitive impairment, and increased risk of functional decline, the toll of ICU delirium is likely to grow exponentially in upcoming decades. This toll is not merely measured in lives lost. Links are increasingly well established between delirium and long-term morbidities, including impaired quality of life, frailty, depression, anxiety, PTSD, and persistent cognitive dysfunction akin to dementia (supporting Aim 4 of MIND-USA). An intervention to reduce delirium may allow more patients not only to survive but also to live more meaningfully.

As a result of the above-mentioned facts, the Society of Critical Care Medicine (SCCM) and numerous others internationally have recommended routine monitoring for delirium in all ICU patients.  Monitoring increases detection and has resulted in earlier and widespread increases in treatment with typical and atypical antipsychotics  despite cautionary studies.  The majority of health care professionals in a national survey conducted in 2002  believed that delirium was a vital yet inadequately addressed problem in critically ill patients and that there were few data directing appropriate therapy for this condition. Unfortunately, only a few randomized trials of any pharmacological interventions in ICU patients have improved our knowledge base,  though we are poised to correct this deficit in our understanding of the efficacy and safety of antipsychotics for delirium.

MIND-USA Protocol Version: 1.15 Confidential Protocol Date: June 22, 2016 5 of 51

Other approaches to managing delirium, such as multicomponent prevention protocols, have been shown in non-ICU populations to improve the incidence and duration of delirium but not mortality.  Unfortunately, none of these studies have included ICU patients and the marked clinical differences of the ICU population (higher number of risk factors for delirium, difficulty with communication due to intubation, and omnipresent use of sedatives) limit the utilization of these protocols in the ever-expanding population of ICU patients.

- 2.2 Aligning Proposed Mechanisms of Delirium with Recommended Therapy. Delirium is thought to result from imbalances in neurotransmitters within the brain.  These imbalances form the fundamental scientific rationale and biological plausibility for our investigation. It is not the purpose of this research, nor would it be possible within such a large trial, to measure or document correction of neurotransmitter imbalances. This section provides a basic introduction to the concepts underlying this study proposal. It is hypothesized that delirium treatment may be achieved by partial correction of neurotransmitter imbalances via haloperidol or ziprasidone, with the secondary aim of minimizing adverse effects. This last point is important because drugs that help correct a neurotransmitter at one site might improve delirium yet cause an adverse event via the same neurotransmitter at another site or via downstream effects on alternative neurotransmitters. 74,75 In general, neurotransmitter imbalances that have received the most attention in literature are dopamine excess, acetylcholine deficiency, and interactions between the serotonergic and dopaminergic systems. Importantly, there appears to be a link between dopaminergic and acetylcholine hypotheses for delirium that support a biological rationale for the MIND-USA study. 76-82 These references and others indicate pharmacological and neuroanatomical evidence that acetylcholine and dopamine appear to be inversely related in delirium pathogenesis. Anatomically, dopaminergic and cholinergic pathways overlap in the brain: D2 receptors for dopamine, which inhibit acetylcholine synthesis, coincide with cholinergic fibers in layer V of the prefrontal cortex. Common events in the ICU, such as hypoxia or hypotension (to be tracked objectively in MIND-USA), can result in surges of dopamine that decrease acetylcholine and precipitate or exacerbate delirium. Neurotransmitter derangements may also be secondary to causal factors that ICU patients frequently possess including severe sepsis, multiple organ dysfunction syndrome, hypoxemia, metabolic disturbances, sleep deprivation, exogenous toxic agents, withdrawal from substances of abuse, and exposure to psychoactive medications, such as narcotics and benzodiazepines, which are indicated but often given in much higher doses and for longer durations than required. Indeed, ICU patients often have greater than 10 risk factors for delirium. 10,16,43,83-86 Critically ill patients experiencing these problems are hypothesized to develop acute brain dysfunction/delirium due to the deranged neurotransmitter levels noted above, a concept that forms the basis of current worldwide (though controversial) practice of treating delirium with typical and atypical antipsychotics, the efficacy and safety of which will be tested in the MIND-USA trial.
- **2.3 State of the Evidence Regarding Haloperidol and Atypical Antipsychotics in Treatment of ICU Delirium**. Haloperidol (used by 75-80% of intensivists) and more recently atypical antipsychotics (used by 35-40%) have emerged as the standard pharmacological treatments for delirium in the ICU.  In the Society of Critical Care Medicine (SCCM)  and other societal guidelines  for the management of pain, anxiety, and delirium in the ICU, haloperidol is recommended as the drug of choice for delirium, though this is based on sparse outcomes data from nonrandomized case series and anecdotal reports. *The dearth of data in this*

MIND-USA Protocol Version: 1.15 Confidential Protocol Date: June 22, 2016 6 of 51

area was emphasized in recent systematic reviews that concluded as follows: (1) "To date, there are no published double-blind, randomized, placebo-controlled trials to establish efficacy or safety of any antipsychotic medication in the management of delirium. There is limited evidence from uncontrolled studies that supports the use of low-dose, short-term treatment of delirium with some antipsychotics. Further study with well-designed clinical trials is required in this area," (2) "Better designed and larger studies evaluating the addition of antipsychotic agents to nonpharmacologic treatments are needed to measure the true effect of pharmacologic treatment," (3) "Small studies of limited scope require further corroborating evidence before translation into specific recommendations for delirium treatment." Consistent with these conclusions, in their newly drafted guideline on the diagnosis, prevention and management of delirium, the National Institute for Health and Clinical Excellence (NICE) has explicitly called for a large, randomized placebo-controlled trial of haloperidol and atypical antipsychotics.

Haloperidol has been touted for over 15 years as a preferred delirium treatment. 90-94 In a 2002 survey of 638 professionals who reported treating delirium with haloperidol or atypical antipsychotics, the top reasons they used these agents were few side effects and satisfactory anecdotal efficacy. Still, over half of the respondents reported witnessing adverse reactions associated with haloperidol. A double-blind, randomized investigation of delirium in AIDS patients found that haloperidol was equal to chlorpromazine regarding delirium outcomes, and both were superior to lorazepam, which exacerbated delirium  (a characteristic of benzodiazepines now shown consistently in ICU patients).  More recently, a large, placebo-controlled prophylaxis study in elderly hip fracture patients (n=430) showed reductions in the severity (p<0.001) and duration (p<0.001) of delirium, but without lowering incidence (~16% in both groups).  A retrospective cohort study concluded that haloperidol in ventilated patients was associated with lower mortality. 97 Atypical antipsychotics—clozapine, ziprasidone, olanzapine, risperidone, aripiprazole, and quetiapine—are used at varying rates anecdotally throughout the world, though very sparse supportive data exist in non-ICU and ICU patient populations. 62,104 Risperidone (in non-ICU patients) 99,103 and olanzapine (in ICU patients) have been randomized against haloperidol, and in both studies there was a temporal reduction in delirium without differences between groups. The olanzapine vs. haloperidol study was an unblinded, non-placebo-controlled trial of 73 low severity and largely non-ventilated ICU patients that concluded olanzapine was a safe alternative to haloperidol. 62 Most recently, in a prospective trial of 36 patients randomized to either quetiapine or placebo (n=18 per group) after having received ~3 to 5 mg of haloperidol, it was found that the haloperidol plus quetiapine treated patients experienced faster resolution of their delirium by 3.5 days as compared with the group receiving haloperidol plus placebo. In addition, the quetiapine-treated patients were over 30% more likely to be discharged home or to rehabilitation than the placebo-treated patients. The lack of a true placebo group in any of these trials precludes any firm conclusions about the role of antipsychotics in ICU delirium.

Regarding survival, however, 5 retrospective studies and 1 prospective placebo-controlled study in non-ICU, non-delirium patients (i.e., predominantly demented elderly cohorts) have reported an association between long-term use (e.g., 2 to 3 months or longer) of both typical and atypical antipsychotics and increased mortality rates (prompting an FDA warning). Whereas both the duration of use and the patient population will be much different in the MIND-USA trial, these reports of increased mortality with antipsychotic use coupled with our data showing rising rates of use of antipsychotics in ICU patients for

MIND-USA Protocol Version: 1.15 Confidential Protocol Date: June 22, 2016 7 of 51

delirium mandate that the medical community confirm the safety of short-term use in ICU patients. Patients adverse effects may be favorably balanced by their short term (days rather than months) exposure meeting the acute need for delirium treatment in a very well-monitored setting, especially in light of alternatives otherwise used such as benzodiazepines.

**2.4 Mechanism and Safety Profile of Antipsychotics**. The mechanism of action of haloperidol is believed primarily to be antagonism at dopamine (D2) and 5HT2A receptors. In addition, its anti-inflammatory effects may help mitigate organ dysfunction in critical illness. Dopamine blockade in the cerebral cortex could improve cognition and reduce delirium. The potent affinity of haloperidol for D2 receptors extends beyond the cortex. Haloperidol also causes concomitant nigrostriatal pathway D2 blockade, disinhibition of acetylcholine (i.e., acetylcholine excess), and a risk for developing EPS acutely and dystonia when used chronically.  In the 2002 survey,  the most frequently mentioned adverse effects of haloperidol were oversedation, EPS, NMS, QT interval prolongation and torsades de pointes, respiratory complications, dystonia, and worsening delirium. Initially, potential adverse effects of haloperidol appeared to exceed those of atypical antipsychotics,  but recent data on adverse events such as EPS, NMS, tardive dyskinesia, glucose and cholesterol abnormalities, cardiac dysrhythmias, and venous thromboembolism appear largely to counter-balance one another between typical and atypical agents  and have called into question the safety profile of both typical and atypical antipsychotics in older patients (especially the demented elderly). 

